Application of defibrillation pads for the second defibrillator will occur during the two-minute cycle of CPR following the third shock with minimal interruptions in CPR. All subsequent defibrillation attempts will be carried out by sequential defibrillation shocks provided by two defibrillators. To ensure shocks are not applied at the exact same moment, we will employ a short (less than one second) delay to provision of the second defibrillator shock. This will be accomplished by a single paramedic pressing the “shock button” on each defibrillator in rapid sequence as opposed to simultaneously. Dispatch deployment strategies will be employed by all paramedic services participating in the trial to ensure two defibrillators are available for all cardiac arrests in the DSED arm of the study. However, in situations when a second defibrillator is not available, the treatment will default to standard defibrillation until such time that a second defibrillator can be secured.

Randomization Strategy

Each cluster (paramedic service) will be randomized to standard defibrillation, defibrillation using VC, or DSED (see attached timeline in **Appendix 2**). All clusters will crossover between standard defibrillation, defibrillation using VC or DSED at least twice per year (at least six distinct treatment periods). Random assignment of treatment sequence will be performed by the coordinating center prior to the start of the study. Specifically, each paramedic agency will perform each arm of the study twice during the duration of the trial. Clusters will not be informed of their group assignments until necessary to make preparations to start the trial or crossover to another study strategy.

Outcome Measures

The primary outcome will be survival to hospital discharge. Secondary outcomes will include neurologic outcome at hospital discharge, ROSC, termination of VF after the first interventional shock, termination of VF inclusive of all interventional shocks, and number of defibrillation attempts to obtain ROSC.

Sample Size

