In response to the need for more efficient trial designs that accelerate discovery and minimize costs, it has been recommended that researchers consider employing multi-arm trials designed for logistical efficiency.²¹ In a multi-arm trial, several treatments are simultaneously assessed against a common control group within a single randomized trial, allowing sizeable gains in efficiency. Relative to conducting separate trials for each experimental treatment, a multi-arm design has been shown to require a lower total sample size and financial resources than separate, sequential two-arm trials.²²

From our internal pilot trial discussed earlier, we observed that across our paramedic services, the annual prevalence of paramedic treated out-of-hospital cardiac arrest for these regions is approximately 4,000; of which 800 (20.0%) patients will present in VF. Our pilot data suggests that approximately 180 patients per year meet the study criteria for refractory VF. Holmen et al.²⁴ demonstrated a 30 day survival rate of 28.7% for patients receiving 1-3 shocks, declining to 12.4% for those receiving 4-10 shocks, and 4.9% for those receiving greater than 10 shocks. Based on these findings, we assumed a baseline survival rate of 12% for patients who will meet our study criteria. This baseline survival rate will be confirmed by comparing to the baseline survival rate of the standard defibrillation arm of the pilot RCT and will be adjusted according to this value.

We hypothesize that DSED and VC defibrillation earlier in the resuscitation will result in survival as high (or higher) as standard defibrillation. We project a minimum absolute increase of 8% in survival to hospital discharge when VC or DSED strategies are employed as per our protocol, compared to standard care.

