Using these baseline estimates, and assuming a fixed number of paramedic service clusters ($n=6$), we will enroll approximately 20-70 patients per cluster over one year. Data from the internal pilot RCT will be included in the final analysis.¹⁷ The study design assumes that each cluster will cross over twice to receive each of three treatment approaches (standard defibrillation, DSED and VC) for approximately six months. We assumed a plausible intra-cluster correlation (ρ) of 0.010 and a plausible inter-period correlation (η) of between 0.008 and 0.010 and without multiplicity correction, as has been recommended for exploratory trials involving multiple treatment arms.^{22,25} Under these conditions, the trial will have adequate power (>80%) with an α level 5%, to detect a minimally important 8% absolute difference in survival to hospital discharge with a sample size of 310 patients per arm (total sample size of 930 patients; approximately 150 patients from internal pilot RCT and 780 patients from the definitive RCT).

Statistical Analysis and Mock Tables (**Appendix 3**):

For this three-arm trial, two treatment strategies (DSED and VC) share a common control arm (standard defibrillation). This approach is chosen to maximize efficiency, allowing comparison of two new treatments to usual care in a single three-armed trial. The primary analysis will compare DSED to standard defibrillation and VC defibrillation to standard defibrillation. A secondary analysis will compare DSED to VC defibrillation. We hypothesize

that resuscitation involving DSED and resuscitation involving VC defibrillation will have superior outcomes compared to resuscitation using standard defibrillation. Because this trial is focused on answering the efficacy question for each treatment strategy separately, and the interpretation of the results of one comparison have no direct bearing on the interpretation of the other. In this situation, no multiplicity adjustment is required.^{22, 25, 26}

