All tests will be 2-sided with $p < 0.05$ denoting statistical significance. The unit of analysis for the comparisons will be the individual patient. All patients will be analyzed according to randomized treatment assignment (intention-to-treat analysis). Based on the DOSE VF pilot RCT secondary analyses will be performed based on actual treatment received, appropriate randomization performed, and appropriate randomization performed with optimal intervention shock timing (shock 4). We will also perform an a priori subgroup analysis comparing rates of survival to hospital discharge for those randomized to DSED who receive DSED after three failed successive standard shocks (early DSED or first DSED shock is shock 4-6) to those who receive DSED after six failed successive standard shocks (late DSED or first DSED shock is shock 7 or later). Last, we will perform a sensitivity analysis to examine the impact of trial phase (pilot study, pre-COVID, and during COVID) on our outcomes. The binary primary outcome, survival to hospital discharge, will be compared across the arms of DSED and VC defibrillation as an adjusted odds ratio with 95% confidence intervals (CIs) using the standard arm as the reference group.²⁷ We will use a generalized linear mixed model (GLMM; logit link) with random effects for cluster-period effect, and using fixed-effects for cluster and for the period, to account for the effect of period on the outcome, as has been recommended for the analysis of cluster crossover trials.^{28,29} The primary analysis will also adjust for the following baseline variables known to impact outcomes after out-of-hospital cardiac arrest: age, sex,

bystander witnessed arrest, bystander CPR provided, time to first arrival, public versus private location, epinephrine and antiarrhythmic use.³⁰ We will also test for effect modification by trial phase, comparing effectiveness in the internal pilot trial and the larger definitive trial. Odds ratios with 95% CIs for secondary outcomes will be calculated in a similar manner, where appropriate.

Consent Waiver

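### The text does not require arms to be balanced within a period although the primary model fits period, and the stated power above 80% is about 76-78% on the plan's own inputs even when period costs nothing

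*Combined protocol and SAP*

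**What the plan says.** All places are in the combined protocol and SAP.

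- **Randomization Strategy.** Each service performs each arm twice over at least six treatment periods. On how sequences are set, it says: "Random assignment of treatment sequence will be performed by the coordinating center prior to the start of the study". It refers to a timeline in Appendix 2. No sentence requires or excludes a set number of services on each arm within a period.
- **Statistical Analysis.** The primary model is a logistic mixed model with a random cluster-period effect, "using fixed-effects for cluster and for the period, to account for the effect of period on the outcome". It also adjusts for several baseline and treatment variables. The coding of period is not described, either for the pilot or for services that joined later.
- **Sample Size.** There are six clusters, and "we will enroll approximately 20-70 patients per cluster over one year". The intra-cluster correlation is 0.010 and the inter-period correlation 0.008 to 0.010. With 310 patients per arm (930 in all, about 150 of them from the pilot), "the trial will have adequate power (>80%) with an α level 5%, to detect a minimally important 8% absolute difference in survival". No formula is given, and neither estimation of period effects nor within-period balance is mentioned.

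**The concern.** Once service and period are both fitted as fixed effects, the treatment effect is estimated only from the variation in arm that is left within services and within periods. If a period has most services on one arm, part of the treatment contrast coincides with the period effect and is removed with it. Balance within a service does not prevent this. Balance across services within each period does.

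With only six services the effect can be large. It depends on the schedule drawn and can differ between the DSED and VC comparisons of the same trial. A power figure computed from the number enrolled and the two correlations alone does not show it. The loss is also avoidable without any extra patients, provided that the schedule is constrained before it is drawn.

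**Working it through.** **1. Inputs.** Control survival: "we assumed a baseline survival rate of 12% for patients who will meet our study criteria". Effect: "We project a minimum absolute increase of 8% in survival to hospital discharge", so 12% versus 20%. Test: "All tests will be 2-sided with $p < 0.05$ denoting statistical significance". From Sample Size: 310 per arm, ρ = 0.010, η = 0.008 to 0.010. Six services by six periods make 36 cells, so the mean cell size is m = 930/36 = 25.8. The service sizes below are assumptions inside the printed range of 20-70 per year.

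**2. The plan's own figure, with period costing nothing.** The cluster-crossover design effect is DE = 1 + (m − 1)ρ − mη.
- η = 0.010: DE = 1 + 0.2483 − 0.2583 = 0.990.
- η = 0.008: DE = 1 + 0.2483 − 0.2067 = 1.042.

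SE = √[(0.12×0.88 + 0.20×0.80)/310 × DE] = √[0.2656/310 × DE], and power = Φ(0.08/SE − 1.96).
- η = 0.010: SE = 0.02912, power = Φ(0.787) = 78.4%.
- η = 0.008: SE = 0.02987, power = Φ(0.718) = 76.4%.

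Pooled variance gives 78.1% and 76.0%. The number per arm for 80% is 322 to 343 over the two values of η and the two variance forms, against 310 planned. The stated figure is not reproduced.

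**3. Cost of fitting period, equal service sizes, independent sequences.** With 36 cells and six service effects, 30 within-service degrees of freedom remain. Five period contrasts take 5/30 = 1/6 of the information on average, so efficiency is about 0.83. With no residual clustering (DE = 1), 0.08/SE = 2.733 and power without period terms is Φ(0.773) = 78%. At efficiency 5/6 it is Φ(2.733×√0.833 − 1.96) = Φ(0.535) = 70%.

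**4. Unequal sizes.** I drew schedules at random and computed the weighted least-squares information for the treatment contrasts with fixed service and period effects, again with no residual clustering.

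| Assumed patients per year | No period terms | Independent sequences | Two services per arm in every period |
|---|---|---|---|
| equal | 78% | 70% | 78% |
| 55/45/35/30/20/20 | 78% | 68% | 77% |
| 70/25/25/20/20/20 | 78% | 66% | 75% |

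The average loss is 8-12 points with independent sequences and 0-3 points with the balanced layout.

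**5. The same with the plan's correlations.** A generalized least-squares version with a random cluster-period variance of ρ − η, for equal sizes and for 70/50/40/30/25/20, gives mean power of 66-70% and a mean loss of 8.4-8.5 points (equal) or 10.1 points (unequal).

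**6. Spread over draws.** Against the balanced layout, the 5th to 95th percentile of the loss runs from about 1-2 to 19-24 points. This covers both size sets and two ways of drawing: any order, or each arm once in each half. Exact balance in every period occurred in 0 of 20,000 independent draws, and in 81% at least one period had no service on one of the arms. Within one schedule the DSED and VC powers differed by about 5-6 points on average.

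**7. Late entry.** Only four of the six services were in the pilot. If two services are assumed to start three periods later and period is coded by calendar, the mean loss with independent sequences is 14-15 points.

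**The case against.** The strongest reply is that nobody reading this text can see the schedule. A random assignment of sequences is as consistent with a draw from balanced schedules as with six independent draws, and Appendix 2, to which the section refers, is not in the text available. This stands. A reader might infer that the sequences were in fact unbalanced and that the trial lost 8-12 points. The documents do not support that: only one schedule was used, and its loss could be close to zero.

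Nor can it be said that the sample size assumed a period-balanced layout. The paragraph gives no formula and its figure is not reproduced, so the method is unknown. One can say only that no allowance for period is shown.

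A reader might also take 66-70% as the power of the primary analysis. It is not. The calculations use a linear approximation and omit the covariates, which may change power in a direction the plan does not quantify. The coding of period is assumed as well.

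On the best-case figure, a slightly lower baseline would rescue it. At 11% versus 19% and η = 0.010, SE = √[(0.11×0.89 + 0.19×0.81)/310 × 0.99] = 0.02836 and power = Φ(0.861) = 80.5%. Sample Size does say that the baseline would be checked against the pilot and adjusted, but the value printed is 12%.

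Finally, full recovery by rebalancing applies only to a trial that has not started. If earlier periods came from independent draws, the remaining periods could all have two services per arm, with each service still performing each arm twice, in only about 8-12% of cases. Pilot periods with four services cannot be split evenly over three arms at all.

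**Conclusion.** The concern holds in a conditional form. The text guarantees balance within service only, the primary model fits period, and no allowance for this is shown. Whether anything was lost depends on a schedule that cannot be seen.

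The firm part does not depend on the schedule: on the plan's printed inputs and without covariate adjustment, 310 per arm gives about 76-78%, not more than 80%, even when period costs nothing. There is therefore no slack to absorb a further loss.

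The conditional part is a further 8-12 points on average if sequences were drawn independently over common periods, with about 1 to 24 points for a single draw, and about 0-3 points if two services are on each arm in every period. These sizes rest on assumed service sizes within 20-70 per year, six common categorical periods and a normal approximation on the risk-difference scale.

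**What to change.** 1. **Sample Size.** Replace the claim of more than 80% with power computed from the primary model (fixed service and period effects, random cluster-period effect), using the actual Appendix 2 schedule and the expected service sizes. State how period is coded for the pilot and for later-joining services. Report DSED versus standard and VC versus standard separately.
2. **Randomization Strategy.** State whether the Appendix 2 schedule is balanced within periods. If it is, one sentence closes this part. If it is not, draw at random from schedules that keep each arm twice per service and put two services on each arm in every common period, with the largest services spread over arms. For a trial under way, come as close to this as possible in the periods not yet started.

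**Cost.** No patients or procedures are added. The power figure becomes less favourable, and the last services' sequences become partly predictable from the others. That matters little, because services learn their assignment only when they need to prepare and every service receives every arm. Completed periods and the four-service pilot periods cannot be rebalanced, so only part of any loss is recoverable once the trial is running. The appended monitoring board letter of January 2022 recommends stopping everywhere except one service, which would finish its current arm. If that was followed, item 2 has little left to act on and item 1 is the part that still matters.

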Methods: This will be a three-arm, cluster randomized trial with crossover conducted in six regions of Ontario, Canada (Peel, Halton, Toronto, Simcoe, London and Ottawa) over a three year period of time. According to randomized cluster assignment, all adult (≥ 18 years) patients presenting in refractory VF (defined as patients presenting in VF/pVT and remaining in VF/pVT after three consecutive standard defibrillation attempts each separated by 2 minutes of CPR) during out-of-hospital cardiac arrest of presumed cardiac etiology will be treated by one of three strategies: (1) continued resuscitation using standard defibrillation; (2) resuscitation involving DSED; or (3) resuscitation involving VC (change of defibrillation pads from anterior-lateral to an anterior-posterior pad position) defibrillation. The primary outcome will be survival to hospital discharge. Secondary outcomes will include neurologic outcome at hospital discharge, return of spontaneous circulation (ROSC), termination of VF after the first interventional shock, termination of VF inclusive of all interventional shocks, and number of defibrillation attempts to obtain ROSC. Based on our previous cohort study research and the DOSE VF pilot RCT, we will also perform an a priori subgroup analysis comparing rates of survival to hospital discharge for those randomized to DSED who receive DSED after three failed successive standard shocks (early DSED or first DSED shock is shock 4-6) to those who receive DSED after six failed successive standard shocks (late DSED or first DSED shock is shock 7 or later).

Impact: A well-designed randomized controlled trial employing a standardized approach to alternative defibrillation strategies early in the treatment of refractory VF is urgently required to determine if the treatments of VC defibrillation or DSED impact clinical outcomes.

Background:

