Based on our preliminary work, our research group obtained funding from the Laerdal Foundation to conduct an internal pilot trial of the DOSE VF protocol (<https://clinicaltrials.gov/ct2/show/NCT03249948>) previously approved by the Sunnybrook Health Sciences Center REB. The pilot trial was designed to determine the feasibility of conducting a full-scale randomized trial in this population.^{17,18} The pilot RCT completed on September 9, 2019, trained over 2,500 paramedics in the technique of DSED and vector change defibrillation (VC). The pilot took place in four paramedic services in Ontario (Toronto, Peel, Halton and Simcoe) with all services actively enrolling patients. All paramedics received in-person training using a combination of didactic, video and simulated scenarios prior to the study launch. All eligible patients with refractory VF (n=152) in the participating paramedic services have had paramedics successfully apply both VC and DSED. The DOSE-VF Pilot RCT demonstrated that the protocol is feasible with 89.5% of patients receiving the treatment they were randomized to and 90.2% of patients receiving an intervention shock prior to shock 6 in the resuscitation. As well, no safety concerns were noted (no reports of defibrillator damage, skin burns, inadvertent shocking of paramedics or bystanders) and was well accepted by paramedics in the field. We have as well been able to determine the number of cases occurring in each service during the pilot RCT (varying from 1.4-6.1 cases/month) allowing us to accurately calculate the number of patients required to perform an adequately powered definitive RCT. Finally, we observed that the rate of VF termination and ROSC were greater in both

interventions then standard defibrillation. Specifically, in the standard group, 66.6% of cases resulted in VF termination, compared to 82.0% in VC and 76.3% in the DSED group. ROSC was achieved in 25.0%, 39.3% and 40.0% of standard, VC and DSED groups, respectively. The DOSE-VF pilot RCT has established the feasibility of proceeding with a definitive, adequately powered RCT to determine whether employing a standardized approach to alternative defibrillation strategies early in the treatment of refractory VF may impact clinical outcomes.

Objective: The objective of this study is to compare two novel therapeutic defibrillation strategies (DSED and VC) against standard practice for patients remaining in refractory VF during out-of-hospital cardiac arrest.

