This will be a three-arm, cluster randomized trial with crossover conducted in six regions of Ontario, Canada (Peel, Halton, Toronto, Simcoe, London and Ottawa). These six regions were

selected because each has its own paramedic service, and all have previously participated in and successfully completed prehospital resuscitation trials.^{19,20} Two treatment strategies (DSED and VC) will be simultaneously assessed against a common control group (standard defibrillation). This approach has been chosen to maximize efficiency, allowing comparison of two new treatments to usual care in a single three-armed randomized trial.^{21,22}

The clusters will be defined by the paramedic service in each of the six regions and each cluster will crossover at least twice per year to receive one of three treatment approaches (standard care, DSED or VC) for six months. Each service will apply each of the three treatment arms twice over the duration of the study. The annual prevalence of paramedic treated out-of-hospital cardiac arrest for these regions is approximately 4,000; of which 800 (20.0%) patients will present in VF. Our pilot trial suggests that approximately 180 patients per year will meet the study criteria for refractory VF. The study protocol will be approved by each local institutional Research Ethics Board and is registered with clinicaltrials.gov. (<https://clinicaltrials.gov/ct2/show/NCT04080986>).

All adult (≥ 18 years) patients remaining in refractory VF or pVT during out-of-hospital cardiac arrest of presumed cardiac etiology will be eligible for inclusion. Patients suffering a traumatic cardiac arrest, patients with pre-existing do not resuscitate orders and patients in recurrent ventricular fibrillation (defined as secondary presentation of VF or those presenting in VF but did not receive three consecutive defibrillation attempts) will be excluded. Patient's whose initial care was provided by non-participating EMS agencies or fire services will be excluded.

Study Protocol:

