Independent oversight of this study will be provided by a data safety monitoring board (DSMB) consisting of a biostatistician and two clinical experts, unrelated to the trial. The committee will conduct an unblinded interim data safety analysis to assess for lower than anticipated rates of survival between the three treatment groups. The committee will meet at one-year intervals and provide recommendations to the steering committee; however, the responsibility for the final decision regarding a DSMB-recommended course of action will rest with the steering committee.

Once 450 patients have been enrolled in the trial (including patients enrolled during the internal pilot trial), the DSMB committee will conduct an unblinded interim data analysis and will advise if sample size modification is necessary. Sample size modification based on unblinded interim results is relatively well understood and is unlikely to introduce bias or raise major concerns.⁴⁰⁻⁴² Depending on the estimates of the event rate, they may suggest we maintain

the a priori calculated sample size or increase it (but not decrease it). If a sample size increase is warranted due to lower than anticipated event rates, REB approval will be sought from each participating site.

During our interim analysis we will also formally examine stopping the trial for harm only. The decision to stop for harm will be based on a single interim analysis performed after 50% recruitment (n=450). We will use a Haybittle-Peto one-sided P value < 0.0005 as evidence of harm and criteria to stop the trial. This will not impact the alpha for our final analysis.⁴³ We will also monitor adverse events as they occur and take these into consideration during the interim analysis. The decision to stop the trial will be based upon recommendations by the DSMB in discussion with the trial steering committee.

Feasibility and Possible Problems

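### Does an accrual rate of about 180 patients a year over three years contradict the 780 patients the definitive trial needs?

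*Combined protocol and SAP*

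**What the plan says.** The accrual figure appears twice, each time credited to the pilot. Study Design and Population has "Our pilot trial suggests that approximately 180 patients per year will meet the study criteria for refractory VF"; Sample Size has "Our pilot data suggests that approximately 180 patients per year meet the study criteria for refractory VF". Neither sentence names the services covered. In both sections the figure follows annual counts of about 4,000 treated arrests and 800 in VF for the regions concerned.

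On the pilot, the section The DOSE-VF Pilot RCT says "The pilot took place in four paramedic services in Ontario (Toronto, Peel, Halton and Simcoe"), with 1.4 to 6.1 cases a month per service. The definitive trial adds London and Ottawa, making six.

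On size, the Sample Size section asks for 310 per arm, 930 in total: "approximately 150 patients from internal pilot RCT and 780 patients from the definitive RCT". It assumes six clusters and projects 20 to 70 patients per cluster in a year.

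On duration, the abstract's Methods paragraph says "over a three year period of time". Treatment periods last about six months. Randomization Strategy gives "at least six distinct treatment periods" and then "each paramedic agency will perform each arm of the study twice during the duration of the trial".

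On flexibility, the Data and Safety Monitoring Board section says the interim review may lead the board to keep the planned size or "increase it (but not decrease it"). Feasibility and Possible Problems accepts that actual rates may differ from projection and alter the study's duration.

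**The concern.** In Study Design and Population the 180 comes shortly after the description of the six regions, so a reader may well take it as the six-service total. On that reading three years produce 540 patients against a requirement of 780. The sponsor would then have to run for about 4.3 years, close to nine six-month periods, which fits neither the three-year statement nor two turns at each arm. The alternative would be to close after six periods with about 690 patients, pilot included. That would cost roughly 12 to 13 points of power for the planned difference of 12% versus 20%. An underpowered primary comparison, or an understated length and number of crossovers, would be a real planning fault.

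**Working it through.** **The plan's own figure.** 3 arms × 310 = 930; 930 − 150 pilot patients = 780. This agrees with the Sample Size section.

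**What 780 requires.** 780 / 3 years = 260 a year; 260 / 6 services = 43.3 per service-year.

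**Reading A: 180 is the six-service total.**
- Three years: 180 × 3 = 540, which is 240 (31%) below 780.
- Time to 780: 780 / 180 = 4.33 years, or 4.33 × 2 = 8.7 six-month periods.
- Rate per service: 180 / 6 = 30 a year.

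**Reading B: 180 is the total for the four pilot services.**
- Six services by simple scaling (assumption: London and Ottawa enrol at the pilot services' average): 180 × 6/4 = 270 a year.
- Three years: 270 × 3 = 810, which is 30 above 780.

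**Which reading fits the other figures?**
- Pilot rates of 1.4 to 6.1 a month have midpoint 3.75. Over four services, 3.75 × 4 × 12 = 180, the stated figure; over six, 3.75 × 6 × 12 = 270.
- The pilot range annualised is 16.8 to 73.2 per service, close to the 20 to 70 projected per cluster-year. The midpoint of 20 to 70 is 45; 45 × 6 = 270 a year and 45 × 6 × 3 = 810.
- Suppose one service sits at 20 and another at 70, together 90. If six services total 180, the other four share 90, or 22.5 each, almost at the floor. If four services total 180, the other two share 90, or 45 each, the midpoint.

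The midpoint of a range is not the mean of the services, and both 30 and 43.3 lie within 20 to 70. These checks favour Reading B without proving it.

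**What closing after six periods would cost under Reading A.** Total 540 + 150 = 690, or 230 per arm. Method: pooled-variance formula, 12% versus 20%, two-sided 5%, design effect 1 + (m − 1)ρ − mη with ρ = 0.010. All patients are assumed to be spread evenly over 36 cluster-periods.

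| Total | m | η | Design effect | Power |
|---|---|---|---|---|
| 690 | 19.2 | 0.008 | 1.028 | 0.637 |
| 690 | 19.2 | 0.010 | 0.990 | 0.653 |
| 930 | 25.8 | 0.008 | 1.042 | 0.760 |
| 930 | 25.8 | 0.010 | 0.990 | 0.781 |

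The loss is 0.123 to 0.128. It arises only if enrolment stops after the sixth period whatever the count, and the text available for review contains no such rule.

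**The case for a change.** The best case for acting is that nothing in the text settles the denominator. The Sample Size section moves from the 180 to a calculation on six clusters with no visible scaling step, and the nearby regional counts read naturally as six-region figures. The range of 20 to 70 per cluster-year is wide enough for either reading. A clause allowing duration to move covers departures from a projection; it does not say what the projection was. And nine periods would mean each arm three times, which contradicts the sentence specifying twice.

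Much of this stands. The services behind the 180 are not named, the two sentences on the number of periods are not fully aligned, and Reading A cannot be excluded.

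It does not carry the conclusion, for two reasons. First, a four-service pilot could not itself have observed cases in London or Ottawa, and the plan separately gives a six-cluster projection that covers 780. Second, the loss of power needs both the less supported denominator and a closing rule that the available text does not contain. The stated target is 930 and it may not be lowered. The board's letter of January 28, 2022 also treats the crossover requirement as a minimum to be met. The timeline in Appendix 2 was not available for review and may already settle the calendar.

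**Conclusion.** No change follows. The arithmetic behind the concern is right: 180 a year for three years is 540, not 780. The contradiction, however, depends on reading a pilot-derived rate as a six-service total. On the four-service reading the expected yield is about 810 in three years, which supports 780, assuming the two added services enrol at the pilot average. On the six-service reading, a sponsor following the plan keeps enrolling to 930 and takes about 1.3 years longer than stated. That affects logistics and the number of treatment periods, not the estimand, the analysis model or the planned power.

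This is a missing detail in a planning figure that trial staff can fill sensibly from the per-cluster projection in the same section. The board's recommendation in January 2022 to stop at all sites but one rested on pandemic effects on compliance, staffing and training, so this ambiguity did not drive it.
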